
of the user interface and content. We plan one month for modifications prior to beginning the feasibility study.

Aim 2 Approach. In this aim, we will conduct a feasibility trial, in which 40 dementia caregivers will be randomized to receive a computer tablet preloaded with the CARE-well App or preloaded with internet links relevant to dementia and caregiving. Electronic outcome measures (detailed below) administered via REDCap secure web platform will be assessed at baseline and end of intervention (3 months) during each study visit. To measure sustainability of the App, the first 10 caregivers from each group will be offered the tablets for an additional month to monitor usage of the App outside the formal trial. The goal of this aim is to determine feasibility of the intervention, study procedures, and outcome measures.

Participants & Recruitment. Informal caregivers of individuals (aged 18 and older) who are formally diagnosed with mild-moderate Alzheimer's disease or related dementia (e.g., Lewy body dementia, frontotemporal dementia) documented by a neurologist, psychiatrist, or geriatrician will be screened for study eligibility (diagnoses will be confirmed via a release of information signed by the care recipient). Care recipients must be living in the community, not in nursing homes or assisted living facilities. Care recipients cannot have another serious, active medical illness besides dementia. Caregivers will be recruited from the RIH Alzheimer's and Memory Disorders Center and RIH Neuropsychology Program by communication between the patients' clinicians and their caregivers. In this way, we will obtain consent to contact the caregiver. In addition, we will provide letters to clinic patients that will invite their caregivers to participate in the study. Community advertising will also be implemented. We will recruit for 11 months (Month 11-Month 21) and will need to recruit about 3-4 caregivers per month. **In the past FITT-C trial, we had a recruitment rate of 4.7 caregivers per month.**

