Inclusion/Exclusion Criteria. Inclusion criteria include: 1). adequate English-speaking and reading skills; 2). provide at least 4 hours of supervision per day for the care recipient (either directly or by telephone); 3). live in the community (either with the care recipient or without); 4). have provided supervision/assistance for at least six months prior to enrollment and have no plans for to place the care recipient in long term care or to end their role as caregiver within six months of study enrollment; 5). report some degree of distress associated with caregiving, which will be assessed through endorsement of two of nine negative experiences associated with caregiving (feeling overwhelmed or stressed, sad mood/depression, anger/frustration, loss of contact with family and friends, conflict in family or family stress, neglecting own health, demands or pressures from caregiving, exhaustion/fatigue, not taking care of their own needs or other responsibilities); and 6) access to WIFI at home. Exclusion criteria include: 1). major acute medical illness; 2). severe mental illness (e.g., bipolar, schizophrenia); or 3). diagnosed cognitive impairment.

Procedure & Interventions. After screening and consenting, caregivers will complete an electronic baseline assessment (described below) and will be randomly assigned to receive a computer tablet that has the newly developed CARE-Well App or internet links relevant to dementia caregiving for 3 months. We will provide the caregivers with written information about expectations for the App use at orientation and they will be encouraged to use the website links daily. Computer engineers and/or a research assistant will provide IT support for caregivers in both groups. To minimize face-to-face contact during the COVID-19 pandemic, caregivers will remain at home to complete the second and final study 'visit,' which entails completing follow-up assessments within two weeks of intervention completion. Once follow-up assessments are complete, participants will be instructed to send the computer tablet back to RIH using a prepaid package given to them during their initial study visit. Due to time limitations of the current award, the first 10 caregivers in each group will be offered to keep the tablets and continue to use the App or internet links for an additional month to estimate intervention sustainability.

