Outcomes and Analyses. The primary goal of this project is to demonstrate feasibility of the CARE-Well App and study procedures to support a future trial. As such, the study is not

powered to determine efficacy, but rather to determine 1) whether a future trial will be successfully conducted; and 2) whether an in-person caregiver intervention can be reasonably adapted into a mobile App. We will focus on the following (benchmarks in parentheses):

- Identify the best recruitment sites and methods (% who enrolled from each source and % contacts received from each recruitment method)
- Determine participant willingness to be randomized (% who decline participation because of randomization)
- Establish study enrollment rate and retention (latter variable examined by group)
- Determine adherence to intervention (% of participants who use the App or internet links at least once per day)
- Calculate timing of assessments and completion rates (% of assessments completed within two weeks of study enrollment and intervention completion)
- Determine interest in continuation of tablet/App use (along with frequency of use) after formal trial in a subset of caregivers (10 from each group) as an estimate of sustainability
- Collect ratings of satisfaction with technology and content (% satisfied or very satisfied)

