To establish feasibility for a future trial, we will collect standard dementia caregiving outcome measures at baseline and following the intervention via REDCap secure web platform. We have used these measures extensively in our previous work. These will include demographic characteristics (sex, age, education, race and ethnicity, characteristics of the caregiver (e.g., relationship to recipient, length of caregiving), and care recipient characteristics (e.g., dementia type and severity). We also will collect the following: 1). *Depression: Center for Epidemiologic Studies Depression Scale*, a 20-item self-report inventory (34); 2) *Caregiver burden: Zarit Burden Interview*, a 22-item self-report measure that examines subjective feelings related to the negative impact of caregiving on physical, emotional, financial, and social functioning (35). 3) *Caregiver reaction to problem behaviors: Revised Memory and Behavior Problem Checklist* (36); 4). *Desire to institutionalize: Desire to Institutionalize Scale* (37): six-item scale to assess caregiver planning for long-term placement of the care recipient; 5). *Healthcare resource utilization: Resource Utilization in Dementia - Lite Version* (38); a measure on sexually disinhibited behaviors observed in the care recipient (39).

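### Should interest in continuing be asked of all 40 caregivers, and not only of the first 10 in each group?

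*Protocol*

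**What the plan says.** The protocol's Outcomes and Analyses section lists seven feasibility outcomes. One is to "Determine interest in continuation of tablet/App use (along with frequency of use) after formal trial in a subset of caregivers". It sets the subset at 10 per group and describes the result as an estimate of sustainability.

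Two other sections describe the procedure behind this outcome. Under Aim 2 Approach, "the first 10 caregivers from each group will be offered the tablets for an additional month to monitor usage of the App". Under Procedure & Interventions, "Due to time limitations of the current award, the first 10 caregivers in each group will be offered to keep the tablets" and to go on using the App or the links for one further month, again to estimate sustainability.

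The assessments that apply to everyone are described separately. In Outcomes and Analyses, "we will collect standard dementia caregiving outcome measures at baseline and following the intervention via REDCap secure web platform". Satisfaction ratings are listed there with no restriction to a subset. Under Procedure & Interventions, "Once follow-up assessments are complete, participants will be instructed to send the computer tablet back to RIH", so the 3-month assessment comes before the tablet is returned.

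**The concern.** Read alone, the outcome seems to restrict a simple question to half the sample without cause. The time limit explains why only some caregivers can keep a tablet for a fourth month. It does not explain why only those caregivers would be asked whether they would like to continue, since all 40 are due an electronic assessment while they still have the device.

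The subset is also not a random half. It consists of the earliest entrants, who may differ from later ones. If interest were a questionnaire item, the plan would give up precision and accept selection by entry order for no benefit, in one of its seven feasibility outcomes and its only planned estimate of sustainability.

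**Working it through.** **1. What interest refers to.** Three statements need to be read together.

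| Section | Who | What is done | Purpose |
|---|---|---|---|
| Aim 2 Approach | first 10 per group | offered the tablet for one more month | sustainability, use outside the trial |
| Procedure & Interventions | first 10 per group | offered to keep the tablet and continue for a month | sustainability |
| Outcomes and Analyses | 10 per group | interest in continuing, with frequency of use, after the trial | sustainability |

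The people, the period and the purpose agree. The outcome is the measurement that belongs to the offer: whether it is taken up, and how often the device is then used. Both can be observed only in those who receive the offer. No section describes a stated-interest question that was then confined to 20 people.

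**2. Whether the limit to early entrants is explained.** Recruitment runs over Months 11 to 21, which is 11 months. The required rate is 40/11 = 3.64 per month, in agreement with the stated 3 to 4. The first 20 entrants are therefore reached after about 20/3.64 = 5.5 months, that is 10 + 5.5 = 15.5 months into the project. With 3 months of intervention and 1 extra month they finish at about 19.5 months. The last entrants, at 21 months, finish the intervention at 24 and would finish an extra month at 25. (Two simplifications: the first 10 per group are treated as the first 20 overall, and the follow-up assessment window is ignored.) The award's length is not stated, so the cut-off cannot be checked, but a limit that favours the earliest entrants fits the reason given.

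**3. What asking everyone would gain.** The protocol gives no precision calculation for the subset, so there is no figure to reproduce. Equal allocation (20 per group) and the interest levels below are assumptions. Exact (Clopper-Pearson) 95% limits for x of n are the 2.5% quantile of Beta(x, n - x + 1) and the 97.5% quantile of Beta(x + 1, n - x).

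| Assumed interest | 10 asked per group | 20 asked per group | Width, points |
|---|---|---|---|
| 50% | 5/10: 18.7-81.3 | 10/20: 27.2-72.8 | 63 vs 46 |
| 70% | 7/10: 34.8-93.3 | 14/20: 45.7-88.1 | 59 vs 42 |
| 90% | 9/10: 55.5-99.7 | 18/20: 68.3-98.8 | 44 vs 31 |

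Pooled over groups at 70%, 14/20 gives 45.7-88.1 and 28/40 gives 53.5-83.4 (42 vs 30 points). For a difference of 70% against 50%, the Newcombe 95% interval is -20.2 to 52.6 points with 10 per group and -9.7 to 45.3 with 20. It includes zero in both cases.

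**4. Whether the added item could show if the early entrants are typical.** Comparing 20 early with 20 later entrants on a baseline scale, the 95% half-width for a mean difference is t(0.975, 38) x sqrt(2/20) = 2.024 x 0.316 = 0.64 SD. Only large differences would stand out.

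**The case for a change.** The best case for a change is that the protocol never defines interest, that the stated reason covers the loan of the tablet and not a question, and that one item on an existing questionnaire costs almost nothing. Entry order could matter too. Potential Problems and Alternative Strategies foresees recruiting an initial cohort during Aim 1, and more advertising or reminders if recruitment or use is poor, so early and late entrants may differ in source and in prompting.

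Part of this stands. The word interest is loose, and uptake would be plainer. The first 10 per group are not a random half, and doubling the number asked would narrow the intervals as shown.

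None of it makes the plan wrong. Under the reading that fits all three sections, a question put to all 40 measures something new: the hypothetical intention of people, half of whom are about to return the device. It would remove selection by entry order for that item alone. Observed uptake and use, on which the sustainability estimate rests, would still come from the same early entrants. The doubling is also an upper bound, because it assumes that the later entrants complete the 3-month assessment as fully as the first ones. Finally, the questionnaires are not reproduced, so the protocol does not show whether the satisfaction ratings already touch on continued use.

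**Conclusion.** The concern does not hold. The three sections agree with one another, the restriction follows from the offer of an extra month, and the protocol gives the reason for limiting that offer. The planned result is a descriptive estimate of uptake and use in 20 of 40 caregivers. It is sound as such if it is reported for what it is, the experience of the first entrants.

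The alternative would narrow the exact per-group interval by about 17 points at 50% or 70% interest and about 14 points at 90%. At 70% it would still be 42 points wide. No go/no-go threshold depends on the item, and the study is not powered for efficacy, so no conclusion of the trial would change.

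This rests on reading interest as acceptance of the offer. The protocol does not say so outright, but that reading fits all its statements. The sizes rest on equal allocation, complete 3-month assessments and illustrative interest levels. If the investigators did intend a questionnaire item, asking everyone would be a sensible and cheap refinement, though still a matter of choice.
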